### **I. Research Objectives/Background**

As of 2017, cigarette smoking remained the leading cause of preventable premature death worldwide and the CDC predicts tobacco use will result in more than 8 million deaths per year by 2030. Tobacco use disorder (TUD), like other drugs of abuse, is associated with deficits in prefrontal mediated inhibitory control (IC)—the ability to stop pre-potent behavioral responding. We recently reported findings in JAMA Psychiatry showing that IC task-based functional connectivity (tbFC) between the right inferior frontal gyrus (r.IFG) and thalamus (corticothalamic circuit) mediated the association between IC task performance (i.e. successful trial inhibition) and smoking relapse vulnerability: both in a smoking cessation study and delaying to initiate ad lib smoking in the laboratory. Those findings form the basis of our current work examining brain stimulation strategies to strengthen corticothalamic tbFC, improve IC and increase the odds of smoking abstinence among smokers.

Theta burst stimulation (TBS), a form of repetitive transcranial magnetic stimulation effecting areas stimulated and associated networks, is administered in two forms: a) Intermittent TBS (iTBS) which induces long-term potentiation—putatively strengthening network activity, and b) Continuous TBS (cTBS) which induces long-term depression—putatively dampening network activity. In our crossover pilot study with smokers ( $N=12$ ), participants underwent a baseline fMRI visit while performing an IC task to obtain baseline performance and identify the IC-task related peak cluster in the r.IFG for stimulation in two subsequent TBS experimental visits: 1) iTBS and 2) cTBS (order counterbalance), each 15 min. prior to performing the IC task. A significant effect of condition on IC performance was observed ( $F= 9.49$ ,  $p<.03$ ) where, as compared to baseline, performance: a) improved by 14.4% following r.IFG iTBS ( $D = .81$ ); b) worsened by -8.7% following r.IFG cTBS ( $D = .5$ ); resulting in a total performance difference between the r.IFG TBS conditions of 25.3% ( $D = 1.56$ ). These findings build on the extant literature on the role of the r.IFG in IC, demonstrate feasibility of using single-subject task-related brain activation to administer focal brain stimulation to modulate IC and provides the foundation for this proposal to examine whether: a) r.IFG TBS parametrically modulates corticothalamic tbFC (strengthen

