## VI. Number of Subjects

*Human Subjects Involvement and Characteristics.* We propose to enroll 40 participants that meet inclusion/exclusion criteria in order to obtain 30 complete usable datasets.

TARGETED/PLANNED ENROLLMENT: 40			
Ethnic Category	Sex/Gender		
	Females	Males	Total
Hispanic or Latino	2	2	4
Not Hispanic or Latino	18	18	36
Ethnic Category: Total of All Subjects*	40		
Racial Categories			
American Indian/Alaska Native	0	0	0
Asian	1	1	2
Native Hawaiian or Other Pacific Islander	0	0	0
Black or African American	9	9	18
White	9	9	18
Other	1	1	2
Racial Categories: Total of All Subjects*	20	20	40

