## VII. Study Procedures and Research Design

The UG3 phase is a proof-of-concept study to test mechanistic hypotheses of the acute effects of TBS on corticothalamic inhibitory control (IC) task-based functional connectivity (tbFC), IC task performance and ad lib smoking in the laboratory while preliminarily evaluating safety and tolerability of TBS among individuals with TUD. Clearly defined milestones, focused on iTBS

versus cTBS and baseline on IC circuitry, will be met before proceeding to Phase 2 (UH3), a 4-session (over 2-weeks) randomized iTBS versus cTBS trial to assess smoking behavior over two-weeks post-treatment period.

As shown in Fig. 1, individuals ( $N=30$ ) with TUD will complete a baseline MRI visit and, using a crossover design, be randomly assigned to receive iTBS on one visit and cTBS on the other visit. Following TBS, they will repeat the protocol and then perform the SRT [4]. The effects of TBS on IC brain and behavior and smoking on the SRT, along with safety and tolerability, will be assessed.

**Strategies to Ensure a Robust and Unbiased Approach.** As detailed throughout this section, the proposed study will achieve robust and unbiased results via several design features including: explicit inclusion/exclusion criteria; randomization and blinding; use of validated measures; explicit hypotheses and well-validated analytic strategies; power estimates; and careful consideration of potential confounds. As standard practice in our laboratory, we will maximize participant retention and data collection compliance, while maximizing fidelity by providing participants with training on all task procedures prior to data collection.

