effects of a single session of TBS on neural function and behavior [38, 41], a crossover design with a minimum of a 2-day washout period between TBS session is appropriate for this study [63]. Both the participants and the research technicians, other than the technician administering TBS, will be blinded to the condition order. At the end of each visit, the participant and the researcher will independently complete a form indicating which TBS condition they believe was administered during the session and provide a confidence rating on a scale from 1-10.

**Hypothesis Testing.** All hypothesis testing will be conducted with  $\alpha < .05$ , unless otherwise noted. **Rationale.** Based upon the tenet that iTBS induces LTP and strengthens network activity, our prior published work demonstrating that corticothalamic tbFC mediates the association between successful IC task performance and inhibiting smoking [4], and our pilot data demonstrating r.IFG iTBS improves IC (Fig. 1), we hypothesize that r.IFG iTBS will strengthen corticothalamic tbFC, improve IC and attenuate smoking lapse/relapse.

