**Aim 1. Examine the effects of iTBS on IC neural circuitry and task performance.**

**Hypothesis 1:** As compared to baseline: r.IFG iTBS stimulation will strengthen corticothalamic tbFC and improve IC task performance; whereas r.IFG cTBS simulation will weaken corticothalamic tbFC and result in worse IC task performance. **Behavioral analysis plan:** Following procedures outlined in C.4.a, IC performance data will be analyzed with a repeated-measures ANOVA to examine the effects of Condition (Baseline, iTBS, cTBS). **fMRI data analysis plan:** Following procedures in C.4.b—C.4.d, IC corticothalamic tbFC will be processed and modeled using our validated strategy [4] and then Fisher-transformed correlation coefficients (rZ) scores for each participant during each condition will be fed forward and analyzed in SPSS using a repeated-measures ANOVA to examine the effect of Condition.

**Aim 2. Examine the effects of iTBS on ad lib smoking.** **Hypothesis 2:** As compared to baseline: r.IFG iTBS, will extend the duration of abstinence; whereas cTBS shorten the duration of abstinence during an ad lib smoking lapse paradigm in the lab. **Behavioral analysis plan:** As in [4], time to initiate ad lib smoking during the SRT (see C.4.a.2) will be analyzed in SPSS using a repeated-measures ANOVA to examine the effect of Condition. Main effects of Condition on secondary smoking topography variables (e.g. puff volume (ml) and number of puffs) will be explored.

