*fMRI Scan:* 1) a high-resolution anatomical scan; 2) a 7-minute run of the IC task (see Fig 1); and 3) a six minute resting state BOLD (blood-oxygen-level-dependent).

*Randomization:* This will be a single blind study where participants will be randomized 1:1 to receive one session of either intermittent TBS (iTBS) or continuous TBS (cTBS) following the first fMRI.

*SRT:* The Smoking Relapse task will be administered as described above.

*Experimental Visits 1 & 2:* At the beginning of each of these experimental visits, participants will first: provide an expired breath CO sample in order to assess recent smoking; and, among females, provide a urine sample in which the pregnancy test must be negative. Next, breath alcohol levels will be assessed with a handheld breathalyzer and participants must record a BAL of 0.0. If participants continue to be eligible after the biological samples, they will complete study questionnaires to assess mood and to characterize smoking-related behavior. After this, participants will move on to the first of two fMRI sessions followed by the TMS session and the second the fMRI and SRT task.

*fMRI Scan 1:* 1) a high-resolution anatomical scan; 2) a 7-minute run of the IC task (see Fig 1); and 3) a six minute resting state BOLD (blood-oxygen-level-dependent).

*TMS:* Upon randomization, participants will receive either iTBS or cTBS per the theta burst protocols described above.

*fMRI Scan 2:* 1) a high-resolution anatomical scan; 2) a 7-minute run of the IC task (see Fig 1); and 3) a six minute resting state BOLD (blood-oxygen-level-dependent). The second

*SRT:* The Smoking Relapse task will be administered as described above.

**Analytic Strategy** Behavioral and neural data analysis strategies are found in [1] and detailed below.

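### The Aim 1 group-level models for IC accuracy and corticothalamic tbFC give no role to the same-day pre-TBS run, so the randomised iTBS-vs-cTBS contrast may be less precise than the scheduled data allow

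*Combined protocol and SAP*

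**What the plan says.** Section VII, Experimental Visits 1 & 2, sets the order of each TBS visit: "the first of two fMRI sessions followed by the TMS session", then a second scan and the smoking relapse task (SRT). Both scans contain a run of the IC task. With the separate baseline visit, that is five IC runs per person.

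The Aim 1 behavioural plan states: "IC performance data will be analyzed with a repeated-measures ANOVA to examine the effects of Condition (Baseline, iTBS, cTBS"). The Aim 1 fMRI plan puts one Fisher-transformed connectivity score (rZ) per participant and condition into the same kind of model. Neither plan mentions a pre-TBS value, a period term or an order term.

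Two other places bear on this:

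- The design overview at the start of section VII and the Data Safety Monitoring Plan (section XII) describe a baseline MRI visit and a repeat after TBS. Neither mentions a scan before TBS at the TBS visits.
- Under Statistical Analyses, the IC task paragraph enters every scan into a first-level model, then compares iTBS with cTBS on the BOLD contrast by an ANCOVA whose covariate is not named. It distinguishes that contrast from IC accuracy.

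On carry-over, Randomization and Blinding cites an effect of about one hour and concludes that "a crossover design with a minimum of a 2-day washout period between TBS session is appropriate for this study".

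**The concern.** Baseline always comes first, so iTBS vs cTBS is the only randomised comparison. As Aim 1 is written, it compares post-TBS values from two different days. Whatever differs between those days for one person (sleep, nicotine state, mood, scanner session) stays in the error term, although a reading of it is scheduled shortly before stimulation. The plan also does not say how five runs fill three cells, which leaves an analytic choice open on the outcomes meant to inform the move to UH3.

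The pre-TBS run at the second TBS visit is also the only IC and tbFC measurement that could show a difference left over from the first session, and no summary of it is planned.

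**Working it through.** **Inputs from the documents.** Alpha is 0.05 ("All hypothesis testing will be conducted with" that level; two-sided assumed, since sidedness is not stated). The sample is 30 usable datasets: "We propose to enroll 40 participants that meet inclusion/exclusion criteria in order to obtain 30 complete usable datasets". Section VII lists "explicit hypotheses and well-validated analytic strategies; power estimates; and careful consideration of potential confounds" among its design features, but no power figure, SD or target effect follows, so there is no planned figure to reproduce. The one documented iTBS-vs-cTBS effect is the pilot's (N = 12), "resulting in a total performance difference between the r.IFG TBS conditions of 25.3" percent, D = 1.56; the type of D is not stated.

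**Assumed.** The correlation r between the two within-person differences is not in the documents and is varied.

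**Step 1, variance.** Let D_post and D_pre be a participant's iTBS-visit minus cTBS-visit differences after and before TBS.

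- Post-only contrast: relative variance 1.
- D_post regressed on D_pre: 1 - r².
- Change score D_post - D_pre: 2(1 - r), taking equal variances before and after.

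**Step 2, power at N = 30.** Noncentral t, with 29 df unadjusted and 28 df with the covariate (order term left out). Effects are in SD units of the unadjusted D_post. The unadjusted contrast detects 0.53 with 80% power and has 56% power at 0.4.

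| r | 1 - r² | SE ratio | Detectable effect, adjusted | Power at 0.4, adjusted | Change-score variance, 2(1 - r) |
|---|---|---|---|---|---|
| 0 | 1.00 | 1.00 | 0.53 | 56% | 2.00 |
| 0.3 | 0.91 | 0.95 | 0.51 | 60% | 1.40 |
| 0.5 | 0.75 | 0.87 | 0.46 | 69% | 1.00 |
| 0.7 | 0.51 | 0.71 | 0.38 | 84% | 0.60 |

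The variance reductions are 0%, 9%, 25% and 49%. Simulation (4,000 runs each) gave adjusted power of 60%, 66% and 83% at r = 0.3, 0.5 and 0.7. A plain change score is noisier than post-only whenever r < 0.5.

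**Step 3, what r represents.** With day-to-day variance v and run-to-run variance e, and the same TBS response in everyone, r = v/(v + e), so v = e gives 0.5. If individual response varies, that variance enters D_post only and lowers r. If it equals the rest of the variance of D_post, then r = 0.5/√2 ≈ 0.35 and the cut is 0.5²/2 = 12.5% instead of 25%.

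**Step 4, large effects.** If D = 1.56 is read as a paired effect, the noncentrality is 1.56 × √30 ≈ 8.5 and power exceeds 99% without any covariate. The adjustment matters for smaller effects: post-only power is 56% at 0.4 and 75% at 0.5.

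**Step 5, carry-over check.** Compare (visit 2 pre-TBS minus visit 1 pre-TBS) between the two orders, 15 vs 15, with noncentrality d√(15/2). Power is 26% at d = 0.5, and 80% power needs d of about 1.06.

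**Step 6, whether the scan is done.** The costs do not settle it. Compensation is paid per visit, and the fMRI budget divides evenly either way: $58,500/(30 × 3) = $650 and $58,500/(30 × 5) = $390.

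**The case against.** A reader might infer that no analysis uses the pre-TBS scans. The documents do not support that. Every scan enters a first-level model, and the BOLD ANCOVA could have the pre-TBS scan as its unnamed covariate. The plan also refers to a cited publication for its analysis strategies. What stands is narrower: the Aim 1 group-level models for IC accuracy and rZ state no role for these runs, and the ANCOVA concerns a different outcome.

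A reader might also infer that the noise is demonstrably avoidable, or that it puts the UH3 decision at risk. Neither is shown. The gain is nil at r = 0, r is unknown, and the pilot effect would be detected without adjustment. The milestone thresholds are not given. The pilot is small, however, and covers IC performance only; the documents give no TBS effect size for tbFC, so smaller effects cannot be set aside.

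Nor is carry-over ignored: the plan relies on counterbalancing and a washout of at least two days against an effect of about an hour. The available check is weak and detects only differential carry-over, because carry-over common to both orders cannot be separated from practice. If carry-over did occur, the pre-TBS value at the second TBS visit would itself be affected by treatment, which would weaken the adjustment.

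Finally, the pre-TBS run is not needed to give Hypothesis 1 a reference, since that hypothesis is stated against Baseline and the three-level model contains it. Without sham, post-minus-pre change mixes TBS with practice and fatigue.

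**Conclusion.** The point holds as one of precision and specification. The randomised iTBS-vs-cTBS contrast of IC accuracy and rZ is valid as planned, but a same-visit covariate that the schedule already provides has no stated role. Using it would cut the variance by 0% to 49% for r between 0 and 0.7, and by less than the simple variance model suggests if people respond differently to TBS. This rests on r, which is assumed, on 30 complete datasets, and on the detailed visit schedule being the operative text. It does not imply bias, a failed washout or a changed UH3 decision. It does not extend to Aim 2, because the SRT has no pre-TBS measurement at the TBS visits.

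**What to change.** 1. Reconcile the section VII design overview and section XII with Experimental Visits 1 & 2 on whether a pre-TBS scan is done.
2. If it is, keep the three-level ANOVA in Aim 1 for comparisons with Baseline. For the randomised contrast of IC accuracy and rZ, regress the post-TBS difference (iTBS minus cTBS) on the same-visit pre-TBS difference, with TBS order in the model. Leave the pre-TBS difference uncentred and code order +1/2 and -1/2, so that the intercept is the adjusted effect. Use an equivalent mixed model when a pre-TBS run is missing.
3. Name the covariate in the BOLD ANCOVA.
4. Report pre-TBS values by visit and order, and post-minus-pre change for each condition, as descriptive summaries. State that the first has low power and shows only differential carry-over, and that the second includes practice and fatigue.

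If the detailed schedule stands, this is a change of analysis wording with no new data. It costs one degree of freedom for the covariate and one for order.

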Participant Retention and data collection compliance. We will minimize study drop-out and data loss due to participant burden by contacting participants 1 day prior to each session and provide session-specific details and reminders as needed. Over the study, participants will respond to digitally administered questionnaires regarding mood, craving and smoking over the past 24-hrs. This strategy has proven successful in characterizing self-report affect, craving and smoking behavior [50, 54]. In ongoing NIDA-funded smoking cessation studies by our group, response rates reach >95% following RA verification of compliance over a 4-week trial (R01DA038700); ~80% over 8-12 week trials (R34 DA042228, UG3 DA043231). The current proposed UG3 and UH3 studies both fall within a timeline where we have achieved greater than 95% participant compliance.

Training Session. Following consent, each eligible participant choosing to continue with the protocol will participate in an extensive training session to become familiar with all aspects of the study.

- Inhibitory Control (IC) Task Training. During training, participants will perform one complete 7.2 min. run of the IC task (see C.4.a.) and are required to achieve a minimum of 75% correct responses on “Go” trials and a minimum of 25% correct omissions on “NoGo” trials in order to demonstrate understanding of task instructions. If performance is sub-threshold, the participant will be provided feedback from the researcher and perform an additional practice run. Using this same training strategy in our prior studies with individuals with nicotine, cannabis, cocaine or opioid use disorder ( $N > 250$ ), > 95% of participants have met performance criteria after the 1st training run and, among those participants requiring additional training, 100% of participants met criteria after the 2nd training run.
- Habituation to Scanner Environment. Participants will practice the experimental task while inside of a mock scanner in order to reduce scan-related anxiety and improve scan data quality.
- Practice ad lib smoking. Participants will be introduced to, and practice smoking their preferred-brand cigarette using the Clinical Research Support System (CReSS) Lab smoking topography device to become familiar with smoking through the system and minimize effects of a novel smoking experience during testing.

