**GoGo/NoGo Inhibitory control (IC) Task.** The “GoGo/NoGo” task [4, 44] will serve as the experimental probe to evaluate the mechanistic underpinning of TBS on IC, determine whether or not to proceed from the UG3 mechanistic proof-of-concept project to the fully-powered UH3 phase. fMRI BOLD response will be collected from participants as they perform the task. Participants are instructed to press a button in response to common (gray colored circles: 75% of trials) and rare (yellow colored circles: 12.5% of trials) Go stimuli and inhibit responding to rare NoGo stimuli (blue colored circles: 12.5% of trials). The task provides errors of omission and reaction times during Go trials, controls for novelty detection during processing of rare Go trials (yellow circles) and errors of commission on NoGo trials (blue circles). Behavioral data will be processed and analyzed consistent with our prior work with this task [4]. Prior to analysis, NoGo performance will be corrected by scoring NoGo trials with null response as incorrect when the participant did not respond to the ‘Go’ trial preceding it, in order to control for lapses in attention. Data will then be analyzed in SPSS.

**Smoking Relapse analog Task (SRT).** The SRT was developed by the PI ([name]) and smoking behavior outcomes (time to lapse) shown to be predicted by IC corticothalamic neural-circuitry function [4]. In brief, the SRT is comprised of two phases. The first involves up to 10, six-minute

blocks of randomly presented trials of neutral, smoking and emotional images. Following each block, participants rate their craving on a scale from 1-10 and then choose to earn \$1 for each additional block up to 60 min., or quit the task and smoke a cigarette using a pocket CReSS system in which topography measures are recorded.

[figure not shown]
**Neuroimaging Protocol.** Imaging will be performed on a 3T Siemens Prisma scanner: a high-resolution 3D MPRAGE anatomical sequence will be acquired (matrix = 256, flip angle = 9°, 166 slices, slice thickness = 1 mm); whole brain BOLD contrast sensitive images will be acquired using a multi-band (6) EPI sequence (60 slices, TR=800 ms, TE=30 ms, FOV=216, 2.4 mm^3 voxels). Prior to the acquisition of images, the anterior and posterior commissures will be identified in the mid-sagittal slice of a localizer series, followed by the acquisition of PA and AP field maps, and then followed the acquisition of functional images during the IC task.

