*fMRI IC task data preprocessing.* Similar to our prior analytic strategy using this task [4], fMRI data will be preprocessed using SPM12 to remove noise and artifacts, motion corrected [51], temporally realigned using B-spline interpolation and smoothed with an 8mm FWHM Gaussian filter. Functional images for each participant will be processed in their native space.

*IC Task Modeling.* Preprocessed data will be entered into a first-level, whole-brain analysis using the General Linear Model to examine BOLD response to each of the 5 trials of interest: NoGocorrect (successful inhibition), NoGoincorrect (error of commission), RareGocorrect (novel-target detection), RareGoincorrect (novel-target error of omission), and Goincorrect (error of omission). Each event will be modeled as a delta regressor (onset dur. = 0) and convolved with a canonical hemodynamic response function. Motion will be removed through rigid body rotation and translation and parameters included as covariates. A high-pass filter (128 seconds; .008 Hz) will be applied to remove slow signal drift. To identify successful IC-BOLD response, controlling for novelty detection, a NOGOcorrect–RareGocorrect contrast image (IC-contrast) will be generated [4] and fed forward to ROI identification.

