*fMRI data processing.* Pre-processing of functional images includes: slice-time correction and realignment[18]; motion outlier detection (framewise displacement  $> 4$  mm ( $\sim 1$  acquisition voxel) [www.nitrc.org/projects/artifact\\_detect](http://www.nitrc.org/projects/artifact_detect)) and correction (via nearest-neighbor interpolation); despiking at 4% of global mean ([cibsr.stanford.edu/tools/human-brain-project/artrepair-software.html](http://cibsr.stanford.edu/tools/human-brain-project/artrepair-software.html)); coregistration of functional images to structural image; warping to MNI space using forward deformations, resampling to  $(1.5\text{mm})^3$  voxel size (i.e.,  $3.375\mu\text{L}$ ) and smoothing with a  $(10\text{mm})^3$  FWHM Gaussian filter.

Task-based functional connectivity (tbFC) data processing. Pre-processed fMRI data will be uploaded into the conn14 toolbox ([www.nitrc.org/projects/conn](http://www.nitrc.org/projects/conn)) for denoising and connectivity analyses. Using unsmoothed segmented tissue images, along with functionally-defined regions of interest (ROIs), significant clusters will be exported using MarsBaR ([marsbar.sourceforge.net](http://marsbar.sourceforge.net)) from the NoGocorrect - RareGocorrect ANCOVA model. Mean time-courses from the unsmoothed BOLD signal from each ROI will be characterized with no additional principal components. Confounds (mean white matter, cerebrospinal fluid signal, and motion parameters) will be regressed out of the mean signal for each ROI. A high-pass filter of 0.008 Hz will be performed after confound regression (no detrending).

*Inhibitory Control Network (ICN) Mask.* An ICN mask that was created in WFU Pickatlas ([fmri.wfubmc.edu/software/pickatlas](http://fmri.wfubmc.edu/software/pickatlas)) for previous studies, including R.IFG, bilateral thalamus, STN, preSMA and left primary motor cortex (BA 4 / M1), will be used as an explicit mask in all analyses.

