***Task-based Functional Connectivity (tbFC).*** Corticothalamic tbFC will be assessed at the 2nd level based on 1st level voxel-wise bivariate correlation maps (i.e., Fisher transformed correlation coefficient [rZ-value] maps) [21].

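### Aim 1 connectivity confounds are regressed before the high-pass filter with no drift term, so slow drift, if present, can bias or blur rZ; filtering data and confounds together avoids this cheaply

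*Combined protocol and SAP*

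**What the plan says.** The paragraph on task-based functional connectivity (tbFC) data processing, under Analytic Strategy in section VII, sends the preprocessed data to a connectivity toolbox "for denoising and connectivity analyses". The order of steps is explicit. First, "Confounds (mean white matter, cerebrospinal fluid signal, and motion parameters) will be regressed out of the mean signal for each ROI". Then, "A high-pass filter of 0.008 Hz will be performed after confound regression (no detrending". No drift term is among the listed confounds, and the text does not say whether the confound series are themselves filtered.

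A separate step, the first-level activation model under IC Task Modeling, has its own filter: "A high-pass filter (128 seconds; .008 Hz) will be applied to remove slow signal drift". That model does not produce the connectivity values.

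The final part of Statistical Analyses builds corticothalamic tbFC from "1 st level voxel-wise bivariate correlation maps", Fisher-transformed to rZ. Under Aim 1, each participant's rZ per condition is "analyzed in SPSS using a repeated-measures ANOVA to examine the effect of Condition", with levels Baseline, iTBS and cTBS.

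**The concern.** The confound coefficients are estimated on series that still contain slow drift, but the connectivity is computed only from what lies above 0.008 Hz. If drift helps to determine the coefficients, they need not suit the retained band. Too much or too little of each confound is then subtracted. Because the same confounds are used for both ROIs, the error can enter both and appear as correlation.

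This regression carries much of the motion control. The fMRI data processing paragraph flags motion outliers only above 4 mm framewise displacement, so smaller movement is left mainly to realignment, despiking and this step. Corticothalamic rZ is the neural outcome of Aim 1, and section VII makes progress to the UH3 trial depend on milestones about this circuitry.

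**Working it through.** The documents give no drift size, residual quality-control figure or error rate tied to this step, so there is no planned figure to reproduce. The mechanism was worked out algebraically and sized by simulation.

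**1. Inputs from the documents.** Imaging: "TR=800 ms, TE=30 ms, FOV=216". Run length, from the training section: "participants will perform one complete 7.2 min. run of the IC task". So 7.2 × 60 = 432 s, and 432 / 0.8 = 540 volumes. (The scan lists say 7 minutes: 420 / 0.8 = 525 volumes, which changes little.) Cut-off 0.008 Hz; 30 usable datasets (section VI); α = 0.05; three conditions. *Assumed:* six motion plus two tissue regressors, and all drift and motion sizes.

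**2. Mechanism, one regressor.** Let the confound be x = f + l (fast plus slow) and the ROI signal be y = s + b·f + d, with d slow. Fitting before filtering gives, in expectation,

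error in b = [cov(l, d) − b·var(l)] / [var(f) + var(l)].

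- No drift in the confound (l = 0): error 0.
- Drift in the signal exactly matching the confound (d = b·l): error 0.
- Drift in the confound only (d = 0), var(l) = var(f): error −b/2, so half the fast confound effect stays in the ROI.
- Both drift, not in proportion: error of either sign.

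If x and y are both filtered first, l and d drop out and the error is 0.

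**3. What the filter leaves.** 432 × 0.008 = 3.46 cycles. A DCT (cosine) filter drops terms with k / (2 × 432) < 0.008, that is k < 6.9, so seven terms (k = 0 to 6). It leaves 0.07% of the variance of a linear trend and 0.7% of a quadratic. An FFT-type filter would leave 17% of a linear trend. The documents do not name the type.

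**4. Mean r in a single run, plan's order.** Drift is in units of the signal SD.

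| Assumed drift | True r = 0 | True r = 0.30 |
|---|---|---|
| None | nil | 0.29 to 0.30 |
| Same sign in both ROIs, 0.5 | 0.01 to 0.05 | 0.31 to 0.33 |
| Same sign, 1 | 0.04 to 0.19 | 0.33 to 0.43 |
| Same sign, 2 | 0.14 to 0.47 | 0.39 to 0.63 |
| Half-correlated between ROIs, 0.5 / 1 / 2 | 0.01–0.02 / 0.04–0.07 / 0.13–0.17 | not run |
| Independent between ROIs | −0.01 to 0.00 | not run |
| Only or mainly in the confounds | 0.02 to 0.14 | not run |
| *Data and confounds filtered together, any drift above* | *0.00 to 0.01* | *0.29 to 0.31* |

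A further set of runs with heavier motion gave up to 0.025 for joint filtering. One refinement to step 2: with no trend in the confounds but shared signal drift of 1 or 2 SD, r was 0.33 or 0.41 for a true 0.30. Autocorrelated motion overlaps with the trend by chance.

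**5. Spread.** With independent drift of 1 to 2 SD, the SD of r was 0.06 to 0.33 across sets of runs, against 0.04 to 0.05 with joint filtering. At 1 SD the values included 0.10 to 0.14. Assuming a further session-to-session SD of 0.10 in true r, the variance ratio is (0.10² + 0.14²) / (0.10² + 0.05²) = 0.0296 / 0.0125 = 2.4 at the upper value. At the lowest value (0.06 against 0.04) it is 0.0136 / 0.0116 = 1.2. At 0.5 SD or less the two orders had nearly the same spread.

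**6. Aim 1 test.** N = 30, three conditions, no true effect, same-sign drift, 300 replicates (standard error near 0.05: √(0.05 × 0.95 / 300) = 0.013).

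| Drift at Baseline / iTBS / cTBS | Type I error, plan | Type I error, joint filtering | Mean rZ difference, iTBS − Baseline, plan |
|---|---|---|---|
| 1 / 1 / 1 | 0.03 | 0.04 | 0.00 |
| 0.5 / 0.5 / 0.5 | 0.04 | 0.04 | 0.00 |
| 0.8 / 1 / 1 | 0.20 | 0.06 | 0.04 |
| 0.5 / 1 / 1 | 0.74 | 0.05 | 0.08 |

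The last difference agrees with the single-run results for the same settings: atanh(0.398) − atanh(0.324) = 0.421 − 0.336 = 0.085. The drift imbalance was imposed; it does not come from the documents.

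**The case against.** The plan has a fair defence. The order is stated openly and contradicted nowhere. Regressing before filtering avoids returning removed frequencies through unfiltered regressors. Aim 1 relies on a strategy the investigators describe as validated in earlier work, so keeping it helps comparability. The larger biases above need large drift shared by both ROIs, an assumption unfavourable to the plan. The regression also helps despite its order: in one set of runs it cut spurious r from 0.20–0.40 with no regression to 0.06–0.22. Most importantly, the comparison is within subject with identical processing, so a common bias cancels.

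Most of this stands, and it rules out three stronger readings that a reader might infer.

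- *That the connectivity outcome is contaminated.* The documents give no drift or motion level, so harm is possible but not shown.
- *That omitting detrending leaves drift in the analysed series.* With a DCT-type filter almost none survives; the omission matters only through the coefficients.
- *That the iTBS–cTBS contrast is systematically biased.* Their order is counterbalanced, so visit-order effects favour neither.

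The defence does not cover two things. Joint filtering also avoids returning removed frequencies, so the plan's order gains nothing over it on that point. And cancellation protects neither precision nor the contrast with Baseline. Baseline is always the first experimental visit, with one scan session, whereas each post-stimulation scan is the second of a later visit. Hypothesis 1 is worded against Baseline.

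**Conclusion.** The point holds conditionally. If the confound series carry slow drift, with or without drift in the BOLD signal, the plan's order can misestimate the coefficients in the retained band. The effect on a single run's r is nil without drift, up to about 0.10 when drift is modest, and 0.2 or more when it is large and shared by both ROIs. These figures rest on assumed drift, so they are a range of possibilities and not an estimate for this trial.

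For Aim 1 the exposure is narrower. Precision may be lost with 30 usable datasets, and a false contrast with Baseline may arise if drift or motion differs there. The documents do not show such a difference, and with equal drift the test kept its level (0.03 to 0.04). This is a processing choice that can be improved, not an internal error. Importance is minor to moderate. The conclusion about detrending assumes a DCT-type filter.

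**What to change.** Replace the filter sentence in the tbFC data processing paragraph with:

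> The 0.008 Hz high-pass filter is applied to the BOLD series and to all confound regressors in the same step (simultaneous filtering), or equivalently the low-frequency cosine set is included in the confound regression.

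State the filter type in the same place. The earlier pipeline's order may be kept as a sensitivity analysis for comparability.

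The cost is one processing setting and one sentence, with no new data. The downside is that rZ values will differ slightly from those of the earlier pipeline. In the simulations joint filtering was never materially worse than the plan's order.
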